**1.E. Preliminary Data: Phlebotomy for prediabetes and T2DM).** To demonstrate the benefits of reducing iron on glucose homeostasis, we recently completed a pilot study in which subjects (N=11, 9M and 2F, aged  $57.2 \pm 1.2$  yr, BMI  $30.6 \pm 2$  kg/m^2) with prediabetes (N=3) or early T2DM (N=8) were treated with phlebotomy in order to reduce serum ferritin concentrations. No subjects had evidence of systemic inflammation as assessed by medical history or elevated C-reactive protein. Individuals treated with phlebotomy achieved a significantly lower serum ferritin level with biweekly to monthly 1 Unit donations (average  $3.4 \pm 0.5$  Units, or  $\sim 1.7$  L) of blood, providing further evidence that the elevations in ferritin were related to iron and not inflammation. Women started with lower ferritin ( $92 \pm 2$  ng/mL) compared to men ( $219 \pm 32$  ng/mL,  $p < 0.04$ ) and thus achieved less absolute lowering of their ferritin ( $56 \pm 7$  ng/mL) than did the men ( $150 \pm 33$  ng/mL). Average weights increased slightly but not significantly in both groups over the course of the study (1.8 kg in treated, 3.1 kg in controls,  $p = \text{NS}$ ). Blood hemoglobin concentrations tended to decrease in the treated group ( $p = 0.10$ ); only one subject declined to below the normal range (by 0.1 g/dL, less than 1% below normal) and recovered to normal by the end of the study. There were no serious adverse events and no fainting.

**Improved glucose tolerance after phlebotomy.** Phlebotomy treatment resulted in significant lowering of

area under the glucose curve (AUCg) during a 120 min oral glucose tolerance test (average improvement  $1340 \pm 570$  [mg/dL]\*min,  $p < 0.05$  by paired t test). Non-treated controls increased their AUCg value by an average of  $1110 \pm 670$  (mg/dL)\*min, significantly different from the treated group (Fig. 3,  $p < 0.04$ ). The decrement in the AUCg after phlebotomy tended to be correlated with the starting AUCg value ( $r = 0.667$ ,  $p = 0.13$ ) and the starting ferritin value ( $r = 0.641$ ,  $p = 0.063$ ). AUCg values also trended to decrease more in those with prediabetes than diabetes ( $-10.3 \pm 2.2\%$  compared to  $-2.9 \pm 2.3\%$ ,  $p = 0.06$ ), suggesting that early intervention, perhaps before critical loss of beta cell mass, will prove to have the greater beneficial effect.

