### **Subjects selection criteria**

Subjects will have type 2 diabetes mellitus, or prediabetes, defined by HgbA1C criteria.

- **Inclusion Criteria.** Ages 40-75; At least 3 months since diagnosis of prediabetes or diabetes; HgbA1C value within three months or at screening of 5.7-6.4% for those with prediabetes, undiagnosed on no medication HgbA1C 6.5-6.9 and 7-8.5% for those with diabetes (the upper limit of the latter to reduce the likelihood of major changes in glycemic intervention during the trial period, and the lower limit to allow some room for improvement); Serum ferritin levels within 1 year or at the time of screening in the upper half of the normal range (>50 ng/mL for women and >100 ng/mL for men). C-reactive protein levels up to 11.0. Subjects will be on stable lifestyle therapy and 0-2 antihyperglycemic agents that are non-hypoglycemic (i.e. no sulfonylureas, glinides or insulin) to limit the chances of hypoglycemia if, as hypothesized, participants become more insulin sensitive with iron reduction. Aim 2 – serum ALT> 1.5 times the upper limit of normal, or; liver stiffness of > 12.5 kPa by Fibroscan transient elastography.
- **Exclusion Criteria.** Documented current anemia, hemoglobin levels within 0.5 g/dL of the lower limit of normal (<12.5 g/dL for women and 13.5 g/dL for men), or recent blood loss; bleeding diatheses (coagulation abnormalities or treatment with anticoagulants); serious chronic infections or chronic inflammatory conditions that could elevate ferritin as an "acute phase reactant;" C-reactive protein greater than 10.0, the upper limit of normal, to further validate the lack of significant chronic inflammation; active cancer diagnosis (excluding skin cell cancers other than melanoma); renal insufficiency (eGFR<60 ml/min); history of orthostatic hypotension; heavy alcohol use (NIH criteria, for men greater than 4 drinks on any day or 14/week, for women >3 drinks on any day or > 7/ week); pregnancy or premenopausal women of childbearing age, unless unable to become pregnant because of oral contraceptive use, IUD, birth control implants, surgical loss of ovaries or uterus. Aim 2 – individuals meeting the additional inclusion criteria for aim 2 will be tested for anti-HAV IgM, HBs Ag, anti-HBc. IgM, anti HCV IgM and IgG. Subjects who prove positive for any of these viral serologies, except for HCV IgG will be excluded. The latter will be tested for HCV RNA by PRC, and if negative they will be eligible for enrollment

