- c. Visit 2 (7-14 days) (fasting) (~1 hr):** Report to the Clinical Research Unit (CRU) at University of North Carolina at Chapel Hill (UNC) or Wake Forest (WF) School of Medicine. Review Adverse Events (AE's). Measure outcome variables (weight, blood pressure; blood for, insulin, lipid panel, CMP (14), Ferritin) and the Ultrasound Fibroscan (WFBH site only). Subjects who complete Visit 2 will be compensated \$50 for their time.

*Randomization* (1:1) to control (sham phlebotomy) or phlebotomy groups with final target ferritin levels of 20-40 ng/ml for males and 20-40 for females. Phlebotomy will not be performed if hemoglobin is lower than 12.5 g/dL for women and 13.0 g/dL for men; in that case, subjects will undergo repeat hemoglobin measurement every 2 months. If the hemoglobin value increases above the threshold for phlebotomy at Visits 3 or 4, phlebotomy will be performed; otherwise, participants will have an “end of study” visit 1 at six months. If blood pressure declines by > 20 mm Hg systolic, or pulse increases by > 30 bpm upon standing, phlebotomy will not proceed.

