*Phlebotomy:* Both groups will have a sleep mask-style blindfold placed or a barrier (e.g. a towel) will be placed between all subjects and the phlebotomy bag in order to prevent the subject from knowing if blood was drawn, and have a phlebotomy needle placed, usually in an antecubital vein. The treatment group will have 1 Unit (~500 mL) of blood removed, while in the placebo group the needle will remain clamped. After the usual 8-10 minutes required for removal of the unit, both groups will have the needle removed, be given a zero-calorie rehydration drink (12 oz) and remain seated for at least 5 min or until comfortable to stand. A snack will be offered. Blood pressure will be monitored after the procedure and if there is hypotension by the above criteria (see *Randomization*), the subject will be asked to remain another 5-10 min and encouraged to finish the drink or have a second. The phlebotomies or sham phlebotomies will be performed by research nurses in the CRU, who have the training and support to respond to a medical emergency. For considerations related to phlebotomy safety and the use of the placebo group, please refer Visit 3. *WFBH participants only:* The discarded phlebotomy blood will be de-identified and will be picked up by a representative from the [name], the sample will be stored in the Olin Physical Lab on the Reynolda campus, room 216. The blood will be used for in vitro experiments aiming to prevent thrombosis in extracorporeal circulation devices. An Institutional Review Board (IRB) must also approve any future research study using your blood sample.

*Review of laboratory findings:* Ferritin results will not be routinely available prior to phlebotomy, but will be reviewed 1-3 days after the visit. Once the serum ferritin results reach the target range (20-40 ng/ml), the subject will be moved to the End of Study sequence.

- **d. Visit 3 (8 weeks after Visit 2) (not fasting) (~1 hr.):** Review AE's. Draw blood for ferritin and perform on site determination of hemoglobin. If hemoglobin is lower than 12.5 g/dL for women and 13.0 g/dL for men, phlebotomy will not be performed and subject will be scheduled 8 weeks out for Visit 4. If the serum ferritin results from this visit have reached the target range (20-40 ng/ml), the subject will be moved to the End of Study sequence. If not, the subject will continue to Visit 4. Subjects who complete Visit 3 will be compensated \$50 for their time.

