- **e. Visit 4 (not fasting):** Review AE's. Draw blood for ferritin and perform on site determination of hemoglobin. If hemoglobin is lower than 12.5 g/dL for women and 13.0 g/dL for men, phlebotomy will not be performed and subject will be scheduled 8 weeks out for Visit 5. At this visit, after the sham phlebotomy, all of the Placebo Group will be scheduled to the “end of study” sequence. Three phlebotomies were the average needed for the treatment group in the pilot study to achieve goal ferritin. If serum ferritin results of the treatment group subjects from this visit have reached the target range (20-40 ng/ml), the subject will be moved to the End of Study sequence. If not, the subject will continue to Visit 5. Subjects who complete Visit 4 will be compensated \$50 for their time.
- **f. Visits 5-6, if needed (not fasting):** Hemoglobin and Ferritin will be drawn. If hemoglobin is lower than 12.5 g/dL for women and 13.0 g/dL for men, phlebotomy will not be performed and subject will be scheduled 6 months out to start the End of Study sequence. If the serum ferritin results from Visit 5 have reached the target range (20-40 ng/ml), the subject will be moved to the End of Study sequence. If not, the subject will continue to Visit 6. After Visit 6, all subjects, regardless of serum ferritin results, will move to the End of Study sequence. Subjects who complete these visits will be compensated \$50 for their time per visit.
- **g. End of Study Visit 1 (6 months ± 2 weeks after last phlebotomy visit) (fasting) (~1 hr.):** Patient should come in fasting. Review AE's. Perform outcome measures (blood pressure, weight, CMP (14), CBC platelets no diff., insulin, HgbA1C, CRP, lipid panel, ferritin. Fibroscan (WFBH site only), place CGM, which the subject will mail back in a prepaid mailer. Subjects who complete this visit will be compensated \$100 for their time.

- **h. End of Study Visit 2 (6 months  $\pm$  2 weeks after E.O.S. 2) (fasting) (~1 hr.):** Patient should come in fasting. Review AE's. Perform outcome measures (CGM placement, blood pressure, weight, CMP (14), CBC platelets no diff., insulin, lipid panel, HgbA1C, ferritin, CRP, Fibroscan (WFBH site only)). Place CGM, which the subject will mail back in a prepaid mailer. Subjects who complete this visit will be compensated \$100 for their time.

- Study procedure: Liver Substudy
- The Screening Visit and Visit 1 will be the same as the Basic Study

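### The protocol does not say how masking is kept when Visit 3 or 4 is held for low hemoglobin, so a hold can suggest that the participant is in the treated arm

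*Combined protocol and SAP*

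**What the plan says.** Participants are meant to be masked. Under Interventions and Interactions, the paragraph on the phlebotomy procedure has a blindfold or barrier used in both groups "in order to prevent the subject from knowing if blood was drawn". The arms differ only behind that barrier: "The treatment group will have 1 Unit (~500 mL) of blood removed, while in the placebo group the needle will remain clamped". Allocation is 1:1.

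The hemoglobin hold first appears with randomization at Visit 2: "Phlebotomy will not be performed if hemoglobin is lower than 12.5 g/dL for women and 13.0 g/dL for men". It returns in items d to f of the basic study procedures. At Visit 3, "phlebotomy will not be performed and subject will be scheduled 8 weeks out for Visit 4". Visit 4 has the same rule, with rescheduling to Visit 5. At Visits 5–6 the consequence changes: "phlebotomy will not be performed and subject will be scheduled 6 months out to start the End of Study sequence". Hemoglobin is measured on site at Visits 3 and 4, so the result acts at the same visit. Blood draws and vital signs still take place.

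The sham arm goes to end of study after Visit 4, so only treated participants reach Visits 5–6.

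The hemoglobin exclusion in the selection criteria is "<12.5 g/dL for women and 13.5 g/dL for men". Women therefore have the same figure for entry and for the hold (12.5). For men the hold lies 0.5 g/dL below entry (13.0 against 13.5).

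The protocol does not provide a sham at a held visit, conceal the hemoglobin value or the reason for the hold, or match holds between arms. It does not say that the sham is omitted either.

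**The concern.** The blind depends on every participant going through what looks like the same procedure at each visit. A held visit breaks that pattern, and holds are unlikely to be balanced between arms. One arm gives up about half a litre of blood at each visit and the other does not. Section 1.E reports for the pilot: "Blood hemoglobin concentrations tended to decrease in the treated group".

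The protocol includes the sham because it expects placebo effects. Participants who believe they are treated may change diet, weight-loss effort or medication use. Overweight and obese participants in both arms receive weight-loss counselling at screening. The outcomes include HgbA1C, CGM, weight and stopping of antihyperglycemic drugs. A laboratory HgbA1C limits assessor bias but does not prevent behaviour from changing the value. The Analytical Plan describes no check of blinding.

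**Working it through.** The plan states no hold rate and no measure of blinding, so there is no figure to reproduce. The check has a textual part and an illustration.

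**Two readings of the hold**

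- *The hold covers the procedure in both arms.* The rule is written for subjects and not for one arm, the procedure paragraph describes both groups together, and the visit table has a single phlebotomy row. A held visit then has no needle placement in either arm, and holds should be more frequent in the treated arm.
- *The hold covers real blood removal only, and shams proceed.* The procedure paragraph also names phlebotomies and sham phlebotomies separately, and Visit 4 has controls leave after their sham with no hemoglobin condition. Every hold is then in the treated arm.

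Neither reading keeps the blind.

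**Probability of being treated, given a hold**

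With 1:1 allocation and hold probabilities pT (treated) and pS (sham),

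P(treated | held) = pT / (pT + pS).

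Under the second reading pS = 0, so the probability is 1. Under the first reading, with assumed pT of 9–12% and pS of 1–3%:

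- 0.09 / (0.09 + 0.03) = 0.75
- 0.12 / (0.12 + 0.03) = 0.80
- 0.09 / (0.09 + 0.01) = 0.90
- 0.12 / (0.12 + 0.01) = 0.92

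**What the pilot can support**

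Section 1.E describes 11 subjects treated by phlebotomy, one of whom fell below normal, by 0.1 g/dL. That is 1/11 = 9.1%, with an exact 95% interval of about 0.2% to 41%. The count is against the normal range and not against this trial's hold limits. The pilot took blood every two to four weeks, against every 8 weeks here, and included 9 men and 2 women. It does not fix a hold rate for this trial.

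**Sensitivity to the assumptions (first reading)**

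A simulation of Visit 3 used the protocol's entry and hold limits. The other inputs are assumptions: mean hemoglobin 13.3 or 13.8 g/dL in women and 14.6 or 15.2 in men; between-person SD 1.0; visit-to-visit SD 0.3 or 0.5; remaining drop 8 weeks after one unit of 0.3, 0.6 or 1.0 g/dL. Participants held at Visit 2 were left out.

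| | Held, sham | Held, treated | P(treated given held) |
|---|---|---|---|
| Women | 2–7% | 6–42% | 0.66–0.94 |
| Men | 0.1–1.6% | 0.7–18% | 0.71–0.98 |

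For women the highest value is 0.291 / (0.291 + 0.020) = 0.94. The lowest comes from hold rates of 0.133 treated and 0.067 sham. At Visit 2, before any unit is removed, the hold rate is the same in both arms (about 3–10% in women, 0.2–2% in men) and the probability is 0.50.

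**Visits 5–6**

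Controls leave after Visit 4, so a participant at Visit 5 is treated whether or not the visit is held. The schedule gives this away, and the hold adds nothing.

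**The case against.** The strongest counter-argument is that the text is silent on masking at held visits and does not say that masking is dropped. Several stronger readings are tempting, and the documents do not support them.

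- *A hold tells participants that they are treated.* If the rule covers both arms, sham participants near the limit can be held through ordinary variation. This applies especially to women, whose entry and hold limits coincide. A Visit 2 hold then says nothing about arm, and orthostatic signs can also stop a procedure. Only if shams proceed regardless is a hold conclusive.
- *Held participants go home without a needle and know why.* Blood is still drawn, and nothing says that the hemoglobin value or the reason is disclosed. Nothing says that it is withheld either.
- *About one treated participant in ten will be held.* The pilot cannot carry this, for the reasons given in the working.
- *The entry and hold limits contradict each other.* They serve different purposes and may differ. A gap that varies by sex merits an explanation, but it is not an inconsistency.

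The effect on the primary endpoint may also be small. If 10% of the treated arm were unblinded and each shifted HgbA1C by an assumed 0.3, the arm mean would move by 0.10 × 0.3 = 0.03, against a planned change of about 0.6. That stands as a limit on importance. It does not remove the gap, because behaviour-dependent secondary outcomes are more exposed and masking is the stated reason for having a sham.

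**Conclusion.** The point holds in limited form. Followed as written, the hold rule weakens the participant blind at Visits 3–4 on either reading of the text. If it covers both arms, a hold is a strong but imperfect clue: about 75–92% likely to be the treated arm under the assumed 9–12% and 1–3%, and 66–98% across the wider simulated assumptions. If shams proceed regardless, the clue is complete.

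The direction rests on blood removal lowering hemoglobin, which the pilot supports only as a trend (p = 0.10). The number of participants affected and the resulting bias cannot be derived from the documents, and a material bias in the primary HgbA1C comparison is not shown. The change is worth making because it is cheap and the gap is avoidable.

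**What to change.** Leave the blood-removal hold and its limits unchanged. Add to Visits 3 and 4 that, when the hold applies in either arm, the existing masked procedure is carried out: blindfold or barrier, needle placed and kept clamped, same duration. This should be subject to the investigator's safety judgement. State that the reason for the hold is not disclosed to the participant unless clinical action is needed, and make explicit that the hold rule applies to both arms. Report held visits by arm and visit.

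The cost is protocol wording, with any consent and ethics review that it requires, and one needle placement without blood removal per held visit. The procedure, staff and visit slot already exist.

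Visits 5–6 are outside this fix, since controls have left by then. The sponsor may also wish to explain why the gap between entry and hold limits differs by sex (12.5 and 12.5 for women, 13.5 and 13.0 for men). No limit is proposed here.

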### **Outcome Measure(s)**

The primary endpoint will be an improvement in glycemia as assessed by HgbA1C at the first end of study visit, 6 months after phlebotomy. Acutely, HgbA1C will be lowered by blood donation, because that test measures the lifetime exposure of a red blood cell (RBC) to glucose; phlebotomy will result in new RBC synthesis and hence younger RBC, but that effect should disappear soon after the normal RBC lifespan of ~3.5 to 4 months, well before the first post-treatment assessment at 6 months.

A secondary endpoint will be HgbA1C at 12 months to probe longevity of the effect. Based on animal data, we expect that value to be further improved relative to 6 months, but we have no human data on which to support that hypothesis. We do not anticipate that the effect will decline over that time based on reaccumulation of iron. This is a slow process: In individuals with hemochromatosis, for example, iron overload and its adverse effects may not appear until the 5th or 6th decades. In fact, we even anticipate continued improvement as the high levels of tissue iron redistribute and re-equilibrate as processes triggered by decreasing iron proceed, such as autophagy of ferritin complexes, and unloading of macrophages in the face of low hepcidin (Fig. 1).

Fasting glucose will also be assessed at 6 and 12 months after phlebotomy, with secondary endpoints being an improvement at 6 and 12 months. CGM will also be performed using the Abbott Freestyle Libre Pro system for 7-14 days to enhance validation of HgbA1C measures; it allows determination of multiple fasting levels, daily average glucose and various indices of glucose excursions, e.g. postprandial maxima and areas under the curve.

Other secondary endpoints include improvement in insulin sensitivity (decreased HOMA-IR calculated from fasting glucose and insulin), discontinuation of oral antihyperglycemic agents because of improved HgbA1C, change in ALT, changes in weight or blood pressure, and conversion from prediabetes (HgbA1C criteria) to either diabetes or normal glucose tolerance. The secondary endpoints were chosen because they are inexpensive and frequently assessed as part of usual clinical care, and because of the literature suggesting that they are also improved by phlebotomy. Outcomes will also be analyzed using initial, final, and change in ferritin as a continuous variable to interrogate possible optimal thresholds and targets for therapy.

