## METHODS AND MEASURES

**DESIGN:** We propose a randomized, placebo-controlled trial to determine if reducing tissue iron stores by phlebotomy (blood donation) will improve measures of glycemia in Type 2 Diabetes (T2DM) or prediabetes. Adult subjects (N=240 total) aged 40-75, half with prediabetes and half with early T2DM (controlled by diet or up to 2 nonhypoglycemic agents) with ferritin values in the upper half of normal will be randomized to receive real or sham phlebotomy (blood donation), performed in the same manner as at Red Cross donation centers. Glycemia will be assessed by HgbA1C (primary endpoint), fasting glucose, and continuous glucose monitoring (CGM) before and after treatment. Glycemic outcomes will be assessed 6 and 12 months after achieving the target ferritin. The primary endpoint for which this study aim is powered is a change in HgbA1C at 6 months. As secondary outcomes, we will determine if that improvement is stable over a year, and if there are changes associated with iron reduction in serum alanine transaminase (index of NASH), insulin sensitivity by homeostasis model assessment (HOMA-IR), weight, lipids, blood pressure, changes in the number of diabetes medications for participants with diabetes, and changes in glycemic status (normal, prediabetes or diabetes) for participants with prediabetes. We will also correlate the degree of change in glycemia with the starting ferritin levels and the overall change in ferritin to determine targets and thresholds for iron reduction.

There will be two optional sub studies that will be conducted only at Wake Forest Baptist Medical Center. One will look more closely at liver complications of diabetes and the other will explore whether improvements in glucose levels are due to more insulin production or improved insulin action.

Iron may also play a role in the progression of fatty liver to scarring and cirrhosis. Since 75% of people with diabetes have some degree of fatty liver, we would also like to study how your liver reacts to the lowering of iron.

This will require some additional test, namely an MRI and a liver Ultrasound (Fibroscan). There will be approximately 40 people recruited at Wake Forest Baptist Medical Center for the liver sub study.

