## **Interventions and Interactions**

*The essential features of interventions and interactions used to generate data for the study should be described.*

- **Intervention:** Periodic (every 8 weeks) phlebotomy of 500 mL (one “Unit”) sufficient to reduce serum ferritin from the upper half of normal to the lowest 20% of normal (Males 20-40, Females 20-40 ng/ml) (35). In our pilot study, subjects reached similar ferritin levels with donation of  $3.4 \pm 0.5$  Units. In that case subjects donated one Unit per month and there were no adverse events; that interval has been increased in this study to 8 weeks to conform to current Red Cross practices.
- **Sham Phlebotomy:** As any other study, interventions are subject to placebo effects, and the same is true for phlebotomy. We are thus including a sham phlebotomy as described in the procedures, below.
- **Study Protocol.** The inclusion and exclusion criteria are listed in **3.A**. We are including arms to address prediabetes and diabetes separately because there is the possibility that the former will respond more robustly to therapy because they will not have had the disease long enough to develop a significant degree of insulin deficiency, a feature of T2DM that may be difficult to reverse in middle-aged or older adults. Our small pilot trial showed improvement in both groups, but 2/3 of those with prediabetes reverted to normal glucose tolerance, a surprisingly good result. For the reason of reversibility cited above, we are not including anyone on insulin; furthermore, anyone on insulin or other agents with the potential to cause hypoglycemia are also excluded because if their insulin sensitivity improves with iron reduction, as the Preliminary Data suggest, they could be more prone to hypoglycemia.

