### **Analytical Plan**

#### **Statistical Plan and Data Analysis.**

The primary analysis will be an analysis of covariance to compare the mean change in the primary endpoint for each aim (HgbA1C at 6 months after phlebotomy for Aim 1, serum ALT at 12 months after phlebotomy for Aim 2, and DI at 6 months after phlebotomy for Aim 3) between the iron depletion and control groups in the full cohort of patients after controlling for the baseline levels of those measurements. The baseline HgbA1C is included as a covariate to increase study power by accounting for regression to the mean between the two time points.

*Secondary Analyses.* The effects of iron depletion on secondary continuous outcomes will be evaluated using analysis of covariance with adjustment for the baseline level of the factor being analyzed as well as the baseline HgbA1C level. For example, we will determine the degree of response (e.g. change in average glucose by CGM) as a function of starting ferritin, ending ferritin, and change in ferritin for determination of dose-response relationships. Treatment effects on dichotomous outcomes (e.g., conversion of pre-diabetes to diabetes) will be evaluated by exact logistic regression, controlling again for the baseline level of the analyzed factor. Ordinal logistic regression will be applied to compare categorical variables with more than 2 ordered categories. In expanded models, interaction terms between the treatment assignment and baseline HgbA1C level will be added to evaluate if the treatment effect differs across the HgbA1C range, and, in particular, between the diabetic and pre-diabetic patients in the study.

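### Drug stops credited to better HbA1c have no time window, although the protocol says phlebotomy itself lowers HbA1c for about 3.5 to 4 months in the treated arm only

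*Combined protocol and SAP*

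**What the plan says.** Outcome Measure(s) acknowledges the artefact: "Acutely, HgbA1C will be lowered by blood donation". It defends the primary endpoint on timing: "that effect should disappear soon after the normal RBC lifespan of ~3.5 to 4 months, well before the first post-treatment assessment at 6 months". Further down, the same section lists "discontinuation of oral antihyperglycemic agents because of improved HgbA1C" as a secondary endpoint, with no time window, confirmation rule or adjudication. The Design paragraph describes the outcome differently, as "changes in the number of diabetes medications for participants with diabetes".

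Only the active arm loses blood. The Phlebotomy paragraph says that "in the placebo group the needle will remain clamped", while the intervention is "Periodic (every 8 weeks) phlebotomy of 500 mL".

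In the Basic Study schedule, HbA1c is drawn at screening (if no recent value exists) and at End of Study 1 and 2. Medications are reviewed at Visits 2 to 6 and at End of Study 1. The one stated measure against therapy changes is the HbA1c ceiling at entry, set "to reduce the likelihood of major changes in glycemic intervention during the trial period". The primary ANCOVA compares arms "in the full cohort of patients after controlling for the baseline levels of those measurements" and says nothing about changes in glucose-lowering drugs.

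**The concern.** The endpoint credits phlebotomy with any stop attributed to a better HbA1c. For much of the time before End of Study 1, a clinic HbA1c in a treated participant can be low because the red cells are young, whatever the glucose is. A sham participant's value has no such error. If a clinician acts on the treated participant's value, the stop meets the stated definition and counts as benefit.

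At stake is a secondary endpoint that readers will take as direct evidence of clinical benefit. If the value that prompted a stop is not recorded at the time, artefactual and genuine stops may not be separable afterwards.

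**Working it through.** The plan gives no expected rate or power for this endpoint, so there is no figure of its own to reproduce. I checked four things.

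**1. Which HbA1c could prompt a stop before End of Study 1?** The study has none between screening and that visit. A qualifying stop in that interval therefore needs a usual-care value. The protocol itself says its secondary endpoints are often measured in usual care.

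**2. How long is the artefact period?** Inputs from the protocol: procedures 8 weeks apart, artefact lasting 3.5 to 4 months (15.2 to 17.4 weeks) after a unit, End of Study 1 at 6 months (26 weeks) after the last procedure. With k procedures:

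- last procedure at week 8(k − 1)
- period ends at week 8(k − 1) + 15.2 to 17.4
- End of Study 1 at week 8(k − 1) + 26

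| Procedures | Period ends (week) | End of Study 1 (week) | Share |
|---|---|---|---|
| 1 | 15.2–17.4 | 26 | 59–67% |
| 3 | 31.2–33.4 | 42 | 74–80% |
| 5 | 47.2–49.4 | 58 | 81–85% |

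This is the share of time in which HbA1c is disturbed, which is not the same as the share in which it is falsely low. I used a simple red-cell model whose inputs are assumptions outside the documents: 8–12% of cells removed on days 0, 56 and 112, regrowth over 6 weeks, lifespan 105 or 120 days, and HbA1c proportional to mean cell age. At a true 7.5%, HbA1c reads roughly 0.3 to 0.7 points low on days 30 to 90. It turns positive from about day 175 as the young cells age, and is near zero by day 294 (week 42). It is more than 0.2 low for roughly 41–55% of the 42 weeks.

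**3. What could this do to the drug-stop endpoint?** Inputs: 240 participants, half with diabetes, randomized 1:1, gives 240 × 0.5 × 0.5 = 60 with diabetes per arm, or 60 × 0.8 = 48 after the 20% dropout allowance. Assumed: 5% stops in sham, no true benefit, and an added percentage of artefactual stops in the treated arm. I enumerated a two-sided Fisher exact test as a stand-in for the planned exact logistic regression. The chance of p<0.05 favouring phlebotomy is:

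| Added artefactual stops | 60 per arm | 48 per arm |
|---|---|---|
| 0 points | under 1% | under 1% |
| 5 points | 9% | 6% |
| 10 points | 33% | 23% |
| 20 points | 85% | 72% |

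**4. What could this do to the primary endpoint?** Suppose 10% of treated participants with diabetes stop an agent and their HbA1c then rises by 0.5 to 1.0 (assumed). The primary pools diabetes and prediabetes, so the shift in the treated mean is 0.5 × 0.10 × 0.5 to 1.0 = 0.025 to 0.05. Against the planned 0.6 that is 4–8%, and it shrinks the apparent benefit. With the SD implied by the pilot (0.6 × 1970/1130 = 1.05) and 96 per arm (120 × 0.8), two-sample power falls from 98% to 95–97%.

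**The case against.** The strongest reply is that the bias is conditional. It needs a usual-care HbA1c in the affected period, a clinician who acts on it, and a drug to stop. The documents give no frequency for any of these. Entry allows 0 to 2 agents, so only part of the diabetes half is exposed. All of this stands, and it is why the percentages above are illustrations only.

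It can also be said that the protocol already deals with the artefact by placing the first assessment at 6 months and adding CGM. The timing does protect the End of Study 1 value: on the plan's figures, 4 months is shorter than 6 months less 2 weeks. It does not protect earlier drug decisions, and neither CGM nor the entry ceiling is tied to which stops count.

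A reader might infer three stronger things, none of which the documents support. One is that the primary HbA1c reading is itself artefactual; the timing argues against this. Another is that clinic HbA1c is falsely low for some 80% of follow-up. That share describes disturbance, and under the assumed model the error changes sign late in the period, so late clinic values could even discourage a stop. The last is that the primary result is seriously distorted. A full-cohort comparison regardless of drug changes is a legitimate treatment-policy analysis, and the shift is small and cannot produce a false positive by this route.

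**Conclusion.** The gap is real but confined to one secondary endpoint. As worded, a stop prompted by red-cell turnover rather than lower glucose counts as benefit, and that artefact arises only in the treated arm. The resulting bias favours phlebotomy for stops prompted by HbA1c values taken while it reads low, among participants with diabetes who take a drug. Its frequency cannot be determined from the documents. If artefactual stops reached 10 points over an assumed 5% sham rate, a trial with no true benefit would show p<0.05 for phlebotomy about a third of the time at 60 per arm.

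For the primary, the expected effect is about 0.025 to 0.05 of the planned 0.6, toward no effect, under the assumptions shown. That justifies a sensitivity analysis but no change to the main analysis. The artefact statement and the discontinuation endpoint, both in Outcome Measure(s), must be reconciled. How background drugs are managed during the artefact period is for the investigators.

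**What to change.** 1. **Endpoint definition.** Count a discontinuation as benefit only if HbA1c, fasting glucose or CGM at End of Study 1 or 2 supports it, with the criterion for support fixed in advance. All three are already scheduled at both visits. A stop prompted by a clinic HbA1c taken between Visit 2 and about 4 months after the last procedure should not count on its own. Use one definition in the Design paragraph and in Outcome Measure(s).

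2. **Recording.** At the existing medication reviews, record the date of each glucose-lowering change and the value that prompted it. The schedule as I can read it shows no medication review at End of Study 2; if that is correct, add one so that stops can be confirmed there.

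3. **Primary analysis.** Keep the ANCOVA and pre-specify a sensitivity analysis that accounts for glucose-lowering drug changes before End of Study 1. Repeating the comparison on CGM mean glucose would not serve, because a participant on less drug would tend to have higher CGM glucose too.

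The cost is a redefined endpoint, two fields on an existing form, one extra analysis and possibly one extra medication review, with no new visit or assay. The drawback is that fewer discontinuations will count, including any genuine early improvement that has been lost by the End of Study visits.
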